9.1 Statistical Analysis Plan Summary

Key elements of the SAP are summarized below. The comprehensive plan is provided in Sections 9.2 through 9.12.

Study Design Overview	A Phase 3, Randomized, Double-blind Study to Compare the Efficacy and Safety of Pembrolizumab (MK-3475) in Combination with Lenvatinib (E7080/MK-7902) Versus Pembrolizumab and Placebo as First Line Treatment for Locally Advanced or Metastatic Urothelial Carcinoma in Cisplatin-ineligible Participants Whose Tumors Express PD-L1, and in Participants Ineligible for Any Platinum-containing Chemotherapy Regardless of PD-L1 Expression (LEAP-011)
Treatment Assignment	
Approximately 694 participants will be randomized in a 1:1 ratio between 2 treatment arms: (1) pembrolizumab + lenvatinib and (2) pembrolizumab + placebo.
 
As of Amendment 011-03, approximately 487 participants have been randomized and no additional participants will be randomized. Stratification factors are as follows:
 
 • Ineligible for any platinum-containing chemotherapy, PD-L1 CPS ≥ 10, ECOG PS 2 • Ineligible for any platinum-containing chemotherapy, PD-L1 CPS < 10, ECOG PS 2 • Cisplatin-ineligible, PD-L1 CPS ≥ 10, ECOG PS 2 • Cisplatin-ineligible, PD-L1 CPS ≥ 10, ECOG PS 0 or 1.
Analysis Populations	Efficacy: Intention to Treat (ITT) Safety: All Participants as Treated (APaT)
Primary Endpoints	
 • PFS per RECIST 1.1 by BICR • OS
Key Secondary Endpoint	
 • ORR per RECIST 1.1 by BICR
Statistical Methods for Key Efficacy Analyses	PFS and OS will be estimated using a stratified Cox regression model. Event rates over time will be estimated within each treatment group using the Kaplan-Meier method. ORR will be estimated by treatment group with 95% CI calculated by Clopper-Pearson exact method.
Statistical Methods for Key Safety Analyses	Point estimates (count and percentage) by treatment group will be provided for safety endpoints.
Interim Analyses	There is no efficacy interim analyses. During the course of the study, DMC performed 6 quarterly safety reviews, including 4 futility analyses. The final analysis will be performed at when approximately 487 participants are randomized.
Multiplicity	There is no multiplicity adjustment.
Sample Size and Power	The total sample size is 487 participants.

9.2 Responsibility for Analyses/In-house Blinding

The statistical analysis of the data obtained from this study will be the responsibility of the Clinical Biostatistics Department of the Sponsor.

This study will be conducted as a double-blind study under in-house blinding procedures. The official, final database will not be unblinded until medical/scientific review has been performed, protocol deviations have been identified, and data have been declared final and complete.

The Clinical Biostatistics Department will generate the randomized allocation schedule(s) for study intervention assignment.

Blinding issues related to the planned interim analyses are described in Section 9.7.

9.3 Hypotheses/Estimation

Objectives and hypotheses of the study are stated in Section 3.

9.4 Analysis Endpoints

Efficacy and safety endpoints that will be evaluated for within- and/or between-treatment differences are listed below, followed by descriptions of the derivations of selected endpoints.

9.4.1 Efficacy Endpoints

Primary

- **Progression-free Survival (PFS):** PFS is defined as the time from randomization to the first documented disease progression (PD) per RECIST 1.1 by BICR, or death due to any cause, whichever occurs first. See Section 9.6.1.1 for the definition of censoring.
- **Overall Survival (OS):** OS is defined as the time from randomization to death due to any cause.

Secondary

- **Objective Response Rate (ORR):** ORR is the percentage of participants with a confirmed CR or PR per RECIST 1.1 by BICR.
- **Duration of Response (DOR):** DOR is defined as the time from the first documented evidence of CR or PR to PD per RECIST 1.1 by BICR or death due to any cause, whichever occurs first.
- **Disease Control Rate (DCR):** DCR is defined as the percentage of participants with a confirmed response of CR, PR, or SD per RECIST 1.1 by BICR. Stable disease must be achieved at ≥ 6 weeks after randomization to be considered a best overall response.

9.4.2 Safety Endpoints

Safety and tolerability will be assessed by clinical review of all relevant parameters including AEs, SAEs, fatal AEs, laboratory tests, and vital signs. Furthermore, specific events will be collected and designated as ECIs as described in Section 8.4.7.

9.4.3 Patient-Reported Outcome Endpoints

As of Amendment 011-03, ePRO endpoints will not be analyzed.

9.5 Analysis Populations

9.5.1 Efficacy Analysis Populations

The analyses of the primary efficacy endpoints are based on the intention-to-treat (ITT) population. All randomized participants will be included in this population. Participants will be analyzed in the treatment group to which they are randomized. Details of the approach to handling missing data are provided in Section 9.6.

9.5.2 Safety Analysis Populations

Safety analyses will be conducted in the All Participants as Treated (APaT) population, which consists of all randomized participants who received at least one dose of study intervention. Participants will be included in the treatment group corresponding to the study intervention they actually received for the analysis of safety data using the APaT population. This will be the treatment group to which they are randomized except for participants who receive incorrect study intervention for the entire treatment period; such participants will be included in the treatment group corresponding to the study intervention actually received. Any participant who receives the incorrect study intervention for one cycle but receives the randomized study intervention for all other cycles, will be analyzed according to the randomized treatment group, and a narrative will be provided for any events that occur during the cycle for which the participant is incorrectly dosed.

At least one laboratory, vital sign, or ECG measurement obtained subsequent to at least one dose of study intervention is required for inclusion in the analysis of the respective safety parameter. To assess change from baseline, a baseline measurement is also required.

9.6 Statistical Methods

9.6.1 Statistical Methods for Efficacy Analyses

This section describes the statistical methods that address the primary and secondary efficacy objectives. Methods related to exploratory objectives will be described in the sSAP. Nominal *p*-values will be computed for other efficacy analyses but should be interpreted with caution because of potential issues of multiplicity.

An OR PD that occurs during Second Course treatment will not be counted as an event for the primary analyses of either endpoint in this study.

9.6.1.1 Progression-free Survival

The nonparametric Kaplan-Meier method will be used to estimate the PFS curve in each treatment arm. A stratified Cox proportional hazard model with Efron's method of tie handling will be used to estimate the magnitude of the treatment comparison (ie, HR) between the treatment arms. The HR and its 95% CI from the stratified Cox model with a single treatment covariate will be reported.

Since disease progression is assessed periodically, PD can occur any time in the time interval between the last assessment where PD was not documented and the assessment when PD is documented. For the primary analysis, for the participants who have PD, the true date of disease progression will be approximated by the date of the first assessment at which PD is objectively documented per RECIST 1.1 by BICR, regardless of discontinuation of study drug.

For the primary analysis, if the events (PD or death) are after more than 1 missed disease assessment, the data are censored at the last disease assessment before missing visits. Also, data after new anticancer therapy are censored at the last disease assessment before the initiation of new anticancer therapy. If a participant meets multiple criteria for censoring, the censoring criterion that occurs earliest will be applied. The censoring rules are summarized in [Table 7](#).

Table 7 Censoring Rules for Primary Analyses of Progression-free Survival

Situation	Primary Analysis
No PD and no death; new anticancer treatment is not initiated	Censored at last disease assessment
No PD and no death; new anticancer treatment is initiated	Censored at last disease assessment before new anticancer treatment
PD or death documented after ≤ 1 missed disease assessment and before new anticancer treatment	Progressed at date of documented PD or death
PD or death documented immediately after ≥ 2 consecutive missed disease assessments or after new anticancer treatment	Censored at last disease assessment prior to the earlier date of ≥ 2 consecutive missed disease assessments and new anticancer treatment

Abbreviation: PD = progressive disease.

9.6.1.2 Overall Survival

The nonparametric Kaplan-Meier method will be used to estimate the OS curve in each treatment arm. A stratified Cox proportional hazard model with Efron's method of tie handling will be used to estimate the magnitude of the treatment comparison (ie, HR) between the treatment arms. The HR and its 95% CI from the stratified Cox model with a single treatment covariate will be reported. Participants without documented death at the time of analysis will be censored at the date of last known contact. Analysis using the Restricted

Mean Survival Time method may be conducted for OS to account for the possible non-proportional hazards effect.

9.6.1.3 Objective Response Rate

ORR will be estimated by treatment group. 95% CI for ORR will be provided using the Clopper-Pearson (exact) method.

9.6.1.4 Analysis Strategy for Key Efficacy Endpoints

A summary of the primary analysis strategy for the key efficacy endpoints is provided in [Table 8](#).

Table 8 Analysis Methods for Key Efficacy Endpoints

Endpoint/Variable	Statistical Method	Analysis Population	Missing Data Approach
Primary Analyses			
PFS per RECIST 1.1 by BICR	Estimation: Stratified Cox model with Efron's tie handling method	ITT	Censored according to rules in Table 7
OS	Estimation: Stratified Cox model with Efron's tie handling method	ITT	Censored at last known alive date
Key Secondary Analyses			
ORR per RECIST 1.1 by BICR	Estimation: Clopper-Pearson (exact) method	ITT	Participants with missing data are considered nonresponders
Abbreviations: BICR = blinded independent central review; ITT = intent-to-treat; ORR = objective response rate; OS = overall survival; PFS = progression-free survival; RECIST 1.1 = Response Evaluation Criteria in Solid Tumors.			

9.6.2 Statistical Methods for Safety Analyses

Safety and tolerability will be assessed by clinical review of all relevant parameters including AEs, laboratory tests, vital signs, and ECG measurements.

Individual events and the broad AE categories consisting of the proportion of participants with any AE, a drug-related AE, a serious AE, an AE which is both drug-related and serious, a Grade 3-5 AE, a drug-related Grade 3-5 AE, a fatal AE, dose interruption due to an AE, discontinuation due to an AE, adverse event of special interest (AEOSI), clinically significant adverse event (CSAE) will be summarized by counts and percentages by treatment group ([Table 9](#)).

Table 9 Analysis Strategy for Safety Parameters

Safety Endpoint	Descriptive Statistics
Any AE	X
Any drug-related AE	X
Any Grade 3-5 AE	X
Any drug-related Grade 3-5 AE	X
Any serious AE	X
Any serious drug-related AE	X
Treatment interruption due to AE	X
Treatment discontinuation due to AE	X
Death	X
Any AEOSI	X
Any CSAE	X
Any Grade 3-5 AEOSI	X
Any Grade 3-5 CSAE	X
Any serious Grade 3-5 AEOSI	X
Any serious Grade 3-5 CSAE	X
Change from baseline results (laboratory test toxicity grade)	X

Abbreviations: AE=adverse event; AEOSI=adverse event of special interest; CSAE=clinically significant adverse event.

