8.4 Adverse Events (AEs), Serious Adverse Events (SAEs), and Other Reportable Safety Events

The definitions of an AE or SAE, as well as the method of recording, evaluating, and assessing causality of AE and SAE and the procedures for completing and transmitting AE, SAE, and other reportable safety event reports can be found in Appendix 3.

Adverse events, SAEs, and other reportable safety events will be reported by the participant (or, when appropriate, by a caregiver, surrogate, or the participant's legally authorized representative).

The investigator and any designees are responsible for detecting, documenting, and reporting events that meet the definition of an AE or SAE as well as other reportable safety events. Investigators remain responsible for following up AEs, SAEs, and other reportable safety events for outcome according to Section 8.4.3.

The investigator, who is a qualified physician, will assess events that meet the definition of an AE or SAE as well as other reportable safety events with respect to seriousness, intensity/toxicity and causality.

8.4.1 Time Period and Frequency for Collecting AE, SAE, and Other Reportable Safety Event Information

All AEs, SAEs, and other reportable safety events that occur after the consent form is signed but before intervention allocation/randomization must be reported by the investigator if the participant is receiving placebo run-in or other run-in treatment, if the event cause the participant to be excluded from the study, or is the result of a protocol-specified intervention, including but not limited to washout or discontinuation of usual therapy, diet, or a procedure.

All AEs from the time of intervention allocation/randomization through 30 days following cessation of study intervention must be reported by the investigator.

All AEs meeting serious criteria, from the time of intervention allocation/randomization through 90 days following cessation of study intervention or 30 days following cessation of study intervention if the participant initiates new anticancer therapy, whichever is earlier, must be reported by the investigator (see Appendix 7 for Germany-specific study requirements).

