9 STATISTICAL ANALYSIS PLAN

NOTE: Efficacy data and non-binding futility boundaries were provided to the eDMC, in addition to safety analyses, to evaluate the benefit/risk ratio of the experimental arm relative to the control arm for LEAP-011 (data cutoff: 26-APR-2021). The interim efficacy data indicated that although the study did not meet non-binding futility boundaries for any of the analyzed endpoints, improvements of outcomes in favor of the combination are unlikely to be as high as initially hypothesized. Based upon these data and the recommendation of the eDMC, Amendment 011-03 was implemented to unblind the study and remove lenvatinib and matching placebo from the treatment arms. The prespecified interim and final analyses of the study described in the statistical analysis plan (SAP) will not be performed. Selected analyses of safety endpoints will be performed at the end of the study; there will be no further analyses of efficacy or ePRO endpoints.

This section outlines the statistical analysis strategy and procedures for the study. If, after the study has begun, but before any unblinding/final database lock, changes are made to primary and/or key secondary hypotheses, or the statistical methods related to those hypotheses, then the protocol will be amended (consistent with ICH Guideline E9). Changes to exploratory or other nonconfirmatory analyses made after the protocol has been finalized, but before unblinding/final database lock, will be documented in a supplemental statistical analysis plan (sSAP) and referenced in the clinical study report (CSR) for the study. Post hoc exploratory analyses will be clearly identified in the CSR. Other planned analyses (ie, those specific to PK/ADA data and PROs) will be documented in separate analysis plans.

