3.6.2 Statistical Methods for Safety Analyses

Safety and tolerability will be assessed by clinical review of all relevant parameters including AEs, laboratory tests, vital signs, and ECG measurements.

The analysis of safety results will follow a tiered approach (Table 4). The tiers differ with respect to the analyses that will be performed. AEs (specific terms as well as system organ class terms) and events that meet predefined limits of change in laboratory, vital signs, and ECG parameters are either prespecified as Tier 1 endpoints or will be classified as belonging to Tier 2 or Tier 3 based on observed proportions of participants with an event.

Tier 1 Events

Safety parameters or AEs of special interest that are identified a priori constitute Tier 1 safety endpoints that will be subject to inferential testing for statistical significance. AEs that are immune-mediated or potentially immune-mediated are well documented and will be evaluated separately; however, these events have been characterized consistently throughout the pembrolizumab clinical development program, and determination of statistical significance is not expected to add value to the safety evaluation. Similarly, the combination

of pembrolizumab and lenvatinib has not been associated with any new safety signals. Therefore, there are no Tier 1 events for this protocol.

Tier 2 Events

Tier 2 parameters will be assessed via point estimates with 95% CIs provided for differences in the proportion of participants with events using the Miettinen and Nurminen method, an unconditional, asymptotic method [Ref. 5.4: 00VMQY].

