Membership in Tier 2 requires that at least 10% of participants in any treatment group exhibit the event; all other AEs and predefined limits of change will belong to Tier 3. The threshold of at least 10% of participants was chosen for Tier 2 events because the population enrolled in this study is in critical condition and usually experiences various AEs of similar types regardless of treatment; events reported less frequently than 10% of participants would obscure the assessment of the overall safety profile and add little to the interpretation of potentially meaningful treatment differences. In addition, Grade 3 to 5 AEs ($\geq 5\%$ of participants in 1 of the treatment groups) and SAEs ($\geq 5\%$ of participants in 1 of the treatment groups) will be considered Tier 2 endpoints. Because many 95% CIs may be provided without adjustment for multiplicity, the CIs should be regarded as a helpful descriptive measure to be used in safety review, not as a formal method for assessing the statistical significance of the between-group differences.

Tier 3 Events

Safety endpoints that are not Tier 1 or 2 events are considered Tier 3 events. Only point estimates by treatment group are provided for Tier 3 safety parameters.

Continuous Safety Measures

For continuous measures such as changes from baseline in laboratory, vital signs, and ECG parameters, summary statistics for baseline, on-treatment, and change from baseline values will be provided by treatment group in table format.

To properly account for the potential difference in follow-up time between the study arms, which is expected to be longer in the combo arm, AE incidence adjusted for treatment exposure analyses may be performed as appropriate.

Table 4 Analysis Strategy for Safety Parameters

Safety Tier	Safety Endpoint	95% CI for Treatment Comparison	Descriptive Statistics
Tier 2	Any AE ($\geq 10\%$ of participants in one of the treatment groups)	X	X
	Any Grade 3 to 5 AE ($\geq 5\%$ of participants in one of the treatment groups)	X	X
	Any serious AE ($\geq 5\%$ of participants in one of the treatment groups)	X	X
Tier 3	Any AE		X
	Change from baseline results (laboratory test toxicity grade)		X
Abbreviations: AE = adverse event; CI = confidence interval; X = results will be provided.			

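### Adverse events are planned as crude percentages by arm although the AE window follows treatment duration; exposure adjustment is optional in the sSAP and absent from the protocol

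*Protocol*

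**What the plan says.** The note opening Protocol Section 9 cuts the remaining work back: "Selected analyses of safety endpoints will be performed at the end of the study". Protocol 9.1 gives the method: "Point estimates (count and percentage) by treatment group will be provided for safety endpoints". Protocol 9.6.2 repeats that the AE categories "will be summarized by counts and percentages by treatment group", and Table 9 has one column, descriptive statistics. Neither place has person-time or a confidence interval.

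The collection window is set in Protocol 8.4.1: "All AEs from the time of intervention allocation/randomization through 30 days following cessation of study intervention must be reported by the investigator". Serious events run to 90 days after cessation, or 30 days if new anticancer therapy starts. Protocol 9.12 summarises exposure as number of cycles, separately from the AE tables.

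sSAP 3.6.2 names the problem, a "potential difference in follow-up time between the study arms, which is expected to be longer in the combo arm", and answers it with "AE incidence adjusted for treatment exposure analyses may be performed as appropriate". It gives no estimator, no definition of person-time and no condition that would trigger the analysis.

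The two documents also differ on precision. In the sSAP, "Tier 2 parameters will be assessed via point estimates with 95% CIs provided for differences in the proportion of participants with events", by the Miettinen and Nurminen method, for events above frequency thresholds (10% for any AE, 5% for Grade 3 to 5 or serious AEs). Protocol Table 9 has no such intervals.

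**The concern.** The proportion of participants with at least one event rises with the time over which events are counted. Here that time is treatment duration plus a fixed tail. If one arm stays on treatment longer, it shows a higher percentage even when the monthly risk is the same. If toxicity shortens treatment in one arm, its percentage is too low. The distortion can therefore imitate toxicity or hide it.

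The only mandatory output is the one affected. The one analysis that addresses time at risk is left to a later judgement of whether it is appropriate. Amendment 03 unblinded the study, so that judgement would be made with treatment assignments known.

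**Working it through.** **1. Design inputs.** The safety sections state no figure to reproduce, so I checked the design values used below. sSAP 3.1 gives 94.7% power for PFS with 558 events, HR 0.7 and one-sided α 0.005. The fixed-design formula gives z = √(558/4) × |ln 0.7| − 2.576 = 11.811 × 0.3567 − 2.576 = 1.637, or 94.9%. It ignores the interim look at 95% of events, so the agreement is good.

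**2. Inputs.** From Protocol 9.9: control median PFS 3.2 months, exponential; 487 randomised 1:1, about 243.5 per arm. From 8.4.1: a 30-day tail, taken as 1 month. My assumptions, not in the documents: treatment ends at progression, and the AE hazard *h* is constant and identical in both arms, at 0.05 or 0.10 per month.

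**3. Crude risk with no difference in hazard.** With exposure exponential at rate μ, risk = 1 − e^(−h) × μ/(μ + h). Control μ = ln 2/3.2 = 0.2166; the combination μ is HR × 0.2166. For example, at HR 0.7 and h = 0.05: combination 1 − 0.9512 × 0.1516/0.2016 = 0.2847; control 1 − 0.9512 × 0.2166/0.2666 = 0.2272.

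| Arm | μ | Mean exposure (1/μ), months | Risk, h = 0.05 | Gap | Risk, h = 0.10 | Gap |
|---|---|---|---|---|---|---|
| Control | 0.2166 | 4.62 | 22.7% | | 38.1% | |
| Combination, HR 0.7 | 0.1516 | 6.60 | 28.5% | +5.7 | 45.5% | +7.4 |
| Combination, HR 0.85 | 0.1841 | 5.43 | 25.2% | +2.5 | 41.4% | +3.3 |
| Combination, HR 1.0 | 0.2166 | 4.62 | 22.7% | 0 | 38.1% | 0 |
| Combination shorter, HR 1/0.85 | 0.2548 | 3.92 | 20.5% | −2.2 | 35.0% | −3.1 |

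Gaps are in points, taken before rounding. Capping treatment at 35 cycles (35 × 21/30.4375 = 24.1 months) changes little: at HR 0.85 and h = 0.05 the gap moves from 2.48 to 2.43 points.

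**4. What confidence intervals would add.** The 95% half-width for a difference near 25% is 1.96 × √(2 × 0.25 × 0.75/243.5) = 7.7 points. An interval on the crude difference keeps the distortion. With the cap and HR 0.7, a control percentage of 30% becomes 36.6%, with standard error 4.3 points. The interval then excludes zero in about 34% of trials with equal hazards. For control percentages of 10% to 70% the figure is 17% to 39%. At HR 0.85 it is 7% to 12%, against 5% when exposure is equal.

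**5. What a single exposure-adjusted rate would do.** Under a constant hazard the rate ratio is 1.00 by construction. If events cluster early it is not. Take a hazard of 0.30 per month in month 1 and 0.02 after, identical in both arms, at HR 0.7.
- Crude risk = 1 − e^(−0.30) × μ/(μ + 0.02): 32.2% control, 34.6% combination.
- Person-months to first event = (1 − e^(−0.30))/0.30 + e^(−0.30)/(μ + 0.02): 3.99 and 5.18.
- Rates per 100 person-months: 32.2/3.99 = 8.1 and 34.6/5.18 = 6.7, a ratio of 0.83.

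The combination falsely looks safer. Splitting person-time at 3 months largely repairs this. Months 1 to 3 add e^(−0.30) × (1 − e^(−2(μ + 0.02)))/(μ + 0.02) = 1.18 and 1.25 person-months to the 0.86 in month 1. The 0–3 month rates become 13.8 and 13.4 (ratio 0.97), and the later rates are 2.0 and 2.0.

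**The case against.** The best defence is that the plan was deliberately reduced. The note in Protocol Section 3 ends formal comparisons between arms, and 9.8 rules out hypothesis testing, so percentages without between-arm intervals fit the smaller scope. The imbalance is already recognised in the sSAP, exposure is summarised in both documents, and Table 9 counts interruptions and discontinuations due to AEs. The sSAP's expectation of longer follow-up sits in text that still plans 694 participants and superiority tests, so it may reflect the original hopes. Protocol Section 9 itself calls improvement of the size first hypothesised unlikely. Treatment beyond progression is allowed, so exposure need not track PFS. Finally, rates assume a roughly constant hazard, while Protocol 6.6.1.1 says immune-related events may come soon after the first dose or months after the last.

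Much of this stands. It limits the size of the problem and rules out a single person-time rate as the whole remedy. Person-time must also be cut when lenvatinib/placebo stops, because Amendment 03 left everyone on pembrolizumab alone. What does not stand is that descriptive status removes the problem: a descriptive percentage by arm still mixes risk with duration. A separate cycle count does not let a reader recover time to first event.

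A reader might infer that the protocol's missing intervals are the main fault and that restoring the Tier 2 intervals would cure it. The documents do not support that. The sSAP still contains those intervals, they match only part of Table 9, and step 4 shows that they do not correct for time at risk.

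**Conclusion.** The concern holds as a gap in the mandatory output: crude percentages, a window tied to treatment duration, an imbalance the sSAP itself expects, and an adjustment that is optional in one document and missing from the other. Its actual size and direction are unknown. The table in step 3 rests on treatment to progression and a constant, equal hazard, and its largest gaps need the original HR of 0.7.

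A reader might infer that the reported safety results will overstate lenvatinib toxicity by six or seven points. The documents do not support this: they give no AE rates or exposure by arm, and the distortion vanishes with equal exposure and reverses with shorter combination exposure. Nor do they support saying that exposure adjustment was never considered, since sSAP 3.6.2 names it. The unreconciled confidence intervals are a separate, smaller inconsistency.

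**What to change.** Keep the crude table. In Protocol 9.6.2/Table 9 and sSAP 3.6.2/Table 4, change *may be performed* to *will be performed* for the main Table 9 categories. Report by arm, descriptively and with 95% confidence intervals:

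- (a) Exposure-adjusted first-event rates. Person-time runs from first dose to first event or the end of the AE window, and is cut at each participant's lenvatinib/placebo stop plus the AE window, so that later pembrolizumab-only time is not counted as combination exposure.
- (b) Either rates by time interval (for example 0–3 and >3 months) or cumulative incidence at fixed times with death as a competing event, because one overall rate assumes a roughly constant hazard.

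Separately, reconcile Protocol Table 9 (no between-arm intervals) with sSAP Tier 2 (Miettinen and Nurminen intervals), and state that intervals on crude differences do not correct for time at risk.

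The cost is amended wording and a few extra descriptive tables from dosing and AE dates already collected. No new participant data are needed.
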